The essential components of a quality orthosis are comfort, efficiency and ease of fitting. Comfort is paramount, as it is directly related patient adherence to treatment. The effectiveness of orthotic treatment can be measured by a reduction in gonarthrosis symptoms or medication use, and potentially an increase in the patient's ability to perform problematic movements. The ease with which the orthosis can be fitted is a component that needs to be optimized, as the user-friendliness of the treatment is important to increase patient adherence to it. The system developed in partnership with Laboratoires Victhom for this project is designed to simplify orthosis fitting, while maintaining comfort and effectiveness.

Research objectives

The aim of this research is to compare two fastening systems for VKB, one consisting of Velcro straps and the other of 3D-printed straps with cable clamping.

With this research, we seek to answer the following questions:

- Is the new cable-tightened belt system as effective at controlling symptoms as the Velcro fastening system currently on the market?
- Is the new cable-tightened strap system more comfortable than the Velcro fastening system currently on the market?
- Does the new fastening system make it easier to install the brace than the one currently on the market?

Our hypotheses are that the new attachment system will be more comfortable and easier to install than the one currently on the market.

Financing

The project was funded by NSERC's *Strengthening College and Community Innovation* program in partnership with Laboratoire Victhom Inc.

Partner company

Laboratoire Victhom Inc.

[name], Vice-President, Research and Development

[name]

[contact]

[contact]

RESEARCH METHODOLOGY

Research location

On TOPMED's premises at [name], Collège Mérici, Quebec City. Impression taking, orthosis delivery and adjustments prior to the trial period will be carried out at the balance clinic ([name]).

Type of test

Repeated measurements on single-factor groups with crossover: Attachment system (2 conditions).

Measurement, assessment and data collection tools

Logbook :

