A new knee brace will be made for each participant. To this end, an impression and anthropometric measurements will be taken during the first meeting with the participant to obtain an orthosis fitted to the patient's leg. Once the orthosis has been assembled, the participant will return to the balance clinic to receive his or her new orthosis. In addition, 3 questionnaires will be completed (ISP + KOOS + PAd1 Satisfaction) and photos of the fitted leg will be taken

Following the delivery meeting, a 14-day wearing period begins. Each time the brace is adjusted at the participant's request, the counter for the adjustment period is reset to zero. This wearing period will always be performed using the Velcro fastening system currently available on the market.

Once the fitting period is over, the first trial meeting will take place(d1). The 1st attachment system (C1) will be installed on the participant's orthosis. The order of attachment system conditions is randomized for participants. In addition, 4 questionnaires will be completed (General Info + ISP + KOOS + PAd14

Satisfaction). A 5th questionnaire (Satisfaction C1j1) will be added if the participant's first trial condition is the cable-tightening attachment system. This questionnaire will be completed after a few minutes' wear of the brace. Photographs of the fitted leg will be taken with all brace systems used during the trial. Following the first trial meeting, the first 14-day trial period begins. During this period, the participant must fill in an electronic logbook on a daily basis.

When the first trial period is over, the second trial takes place (d14). The 1st attachment system(C1) is removed and the 2nd system(C2) is installed on the participant's orthosis. In addition, 4 questionnaires are completed (ISP + KOOS + Satisfaction C1d14 + Satisfaction C2d14). Photos of the fitted leg will be taken, with all attachment systems used during the session. Following this meeting, the second 14-day trial period begins. Again for this period, the participant will be required to complete an electronic logbook on a daily basis.

The third and final trial meeting will take place following the 2nd trial period. The brace will be collected during this meeting. In addition, 4 questionnaires will be completed (ISP + KOOS + C2d28 Satisfaction + Attachment System Comparison). Photos of the fitted leg will be taken during the meeting.

Impression appointment: 45-minute appointment at the clinic.

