Delivery meeting: 1 hour 45 minutes at the clinic. 3 questionnaires will be completed and photos of the fitted leg will be taken.

Adjustment meeting(s): These meetings are optional, will be held at the client's request and last a maximum of 45 minutes.

1st trial session: This session lasts 2 hours at TOPMED. If no change is made to the brace attachment system, 4 questionnaires will be completed. However, if the brace attachment system is changed during the session, 5 questionnaires will be completed. Photographs of the fitted leg will be taken.

2nd trial meeting: This meeting lasts 2 hours at TOPMED, with 4 completed questionnaires and verification of logbooks. Photos of the fitted leg will be taken.

3rd trial meeting: This meeting lasts 1 hour at TOPMED, with 4 completed questionnaires and verification of logbooks. Photos of the fitted leg will be taken. The orthosis will be picked up during this meeting.

PARTICIPATION OF LIVE HUMAN, ANIMAL OR MATERIAL PARTICIPANTS

10 adult participants will be recruited to test the different orthoses. Participants should have mainly worn an ODRA 2.0 orthosis to allow a shorter orthosis fitting period . Participants with lower-limb wounds should be excluded, as wearing the orthosis could aggravate these.

Participant inclusion criteria:

- Be 18 years of age or older;
- Have worn an ODRA 2.0 orthosis for an average of several hours a day over the past 6 months

Participant exclusion criteria:

- People with wounds on the lower limbs.

SCIENTIFIC JUSTIFICATION FOR USING LIVE SUBJECTS

The participation of human participants representative of the clientele is essential for the validation of the new cable-tightening fastening system. Participant feedback will provide us with essential information on the brace's ease of installation, comfort and symptom control, enabling us to confirm the desired properties and, if necessary, modify certain aspects to better match the needs and problems of the target clientele. In addition, the new attachment system needs to be tested on participants to measure the potential biomechanical effects of this new technology

RECRUITMENT

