Vichom Laboratories will contact identified customers to request their consent to share their personal information with the research team. If consent is obtained, the customer's full name and e-mail address will be transferred to TOPMED. These consenting customers will then be contacted by TOPMED with an offer to participate in the current project. Candidates may express their interest by writing to TOPMED. A member of the project team ([name]/[name]/[name], Orthotics-Prosthetics Research Professional) will be available to answer questions, assess eligibility, send documentation and/or set up a telephone appointment at a later date.

RISKS AND DRAWBACKS, AND PROPOSED MITIGATION MEASURES

An allergic skin reaction (redness) due to wearing the brace is a potential injury. The participant should stop wearing the brace, if necessary.

Bruises, corns, scratches and/or pain may appear on the fitted limb, due to poor orthotic fit or incorrect positioning. The orthotist will be present to ensure the best possible fit of the orthosis during the session. Injuries due to appliance breakage are possible.

ADVANTAGES AND BENEFITS

No immediate benefit for participants, except the benefit of trying a new orthosis that could improve their quality of life. The advantage of their participation is that it will provide empirical data on orthosis wear. This is an advantage for Laboratoire Vichom Inc.

FREE AND INFORMED CONSENT

The Information and Consent Form (ICF) will be e-mailed to them once the candidate has shown interest by contacting us again. A period of two (2) weeks will be allowed for reading and reflection. Upon receipt of the signed CIF, the first meeting will be scheduled.

Participants may terminate their participation at any time without negative consequences or prejudice and without having to justify their decision. In this case, participants must inform the responsible researcher or a member of the research team. Thereafter, all material allowing the identification of the participant and the data provided will be destroyed, unless the participant authorizes the researcher to use them for the research despite the withdrawal. In this case, they will be preserved according to the measures described below, which will be applied to all other participants.

CONFIDENTIALITY AND PROTECTION OF PERSONAL INFORMATION

Information collected from questionnaires, photos, logs, anthropometric measurements, videos and gait

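### Does the protocol commit the trial to a single-factor analysis that ignores the period effect of its crossover?

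*Protocol*

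**What the plan says.** The protocol's only statement about design type stands under *Type of test*, between the research location and the data collection tools: "Repeated measurements on single-factor groups with crossover: Attachment system (2 conditions". *Estimated duration of participants' activities* supplies the rest. After delivery of the new brace there is a wearing period of 14 days, with the count restarted at each adjustment the participant asks for. Of this period it says: "This wearing period will always be performed using the Velcro fastening system currently available on the market". Then "The order of attachment system conditions is randomized for participants". "Following the first trial meeting, the first 14-day trial period begins", and at the second trial meeting "The 1st attachment system(C1) is removed and the 2nd system(C2) is installed on the participant's orthosis". "Following this meeting, the second 14-day trial period begins".

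On size, the section on participants says "10 adult participants will be recruited to test the different orthoses". No ratio or blocking of the two sequences is given. *Data processing* covers only the recording of questionnaires and logbooks. No section gives a statistical model, a significance level, a power, a standard deviation or a primary endpoint.

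**The concern.** A reader who takes *Type of test* to mean the statistical test sees one factor, attachment system, and infers a plain paired comparison. The design has two periods and two sequences, and a shift between periods is conceivable: the brace is new, the same questionnaires recur, and the systems are exchanged at one visit without a washout. A paired comparison leaves such a shift in the error term when the sequences are equal in size. When they are unequal, it moves the estimate by the imbalance times the shift. With 10 participants and no stated balancing, unequal sequences are quite possible. The consent section adds a route to imbalance even from a balanced list, because after a withdrawal "Thereafter, all material allowing the identification of the participant and the data provided will be destroyed" unless the participant authorises their use. If the line did fix such an analysis, the main comparison could be underpowered or biased for no good reason.

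**Working it through.** **What the line fixes.** Three readings of the text bear on this.

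1. The label itself contains the word crossover. In a crossover with one experimental factor, the treatment is that factor; period and sequence are features of the layout. Calling the design single-factor is correct and says nothing about which nuisance terms the model will hold.
2. The protocol is a translation, and under *Continuous examination* it uses the word test for the trial itself. *Type of test* therefore reads naturally as type of trial.
3. No model or test statistic follows anywhere. A later analysis with a period term would contradict no sentence of the protocol.

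**What would follow if period were ignored.** The protocol gives no figure to reproduce. Assumptions, none from the documents: SD of the within-person difference = 1, two-sided alpha 0.05, true effect τ = 0 or 1 SD, period effect π = 0 to 1 SD, no carryover.

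Model: d = cable minus Velcro = τ + sπ + e, with s = +1 if cable comes second and −1 if it comes first. Let n1 and n2 be the two sequence sizes, N = 10.

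- Bias without a period term: π(n1 − n2)/N. At 5:5 it is 0. At 7:3 with π = 0.5 it is 0.5 × 4/10 = 0.20 SD. At 8:2 it is 0.5 × 6/10 = 0.30 SD.
- SD inflation without a period term: √(1 + π² × (10/9) × (1 − ((n1 − n2)/10)²)). At 5:5 and π = 0.5 it is √(1 + 0.25 × 1.111) = 1.130; at π = 1 it is √2.111 = 1.453. With the t critical values for 9 and 8 degrees of freedom, the confidence interval ratios to the adjusted analysis are 1.130 × 2.262/2.306 = 1.109 and 1.453 × 2.262/2.306 = 1.425.

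Simulated two-sided type I error of the unadjusted paired t test (200,000 runs per cell), with the chance of each split under simple randomisation, which is an assumption because the method is not stated:

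| Split (either way) | Probability | π = 0.5 SD | π = 1 SD |
|---|---|---|---|
| 5:5 | 24.6% | 3.0% | 0.6% |
| 6:4 | 41.0% | 3.8% | 1.7% |
| 7:3 | 23.4% | 6.0% | 6.3% |
| 8:2 | 8.8% | 10.5% | 20% |

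Averaged over all splits, including 9:1 and 10:0, type I error is 5.0% at π = 0.5 and 5.2% at π = 1. The reason is simple: under simple randomisation s is an independent fair coin for each person, so the differences are independent with mean τ and variance 1 + π², and the paired test is close to valid over the whole procedure. The high rates need 8:2 or worse, which has probability 2 × (0.0439 + 0.0098 + 0.0010) = 11%.

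Power at τ = 1 SD and 5:5, unadjusted against adjusted: 80% v 79% (π = 0), 78% v 79% (0.25), 72% v 79% (0.5), 48% v 79% (1).

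**What adjusting costs.** The adjusted estimate averages the two sequence means, with standard error ½√(1/n1 + 1/n2). Against √(1/10) = 0.316 this is equal at 5:5. At 7:3 it is ½√(1/7 + 1/3) = 0.345, a ratio of 1.09. At 8:2 it is ½√(1/8 + 1/2) = 0.395, a ratio of 1.25. With no period effect, power at τ = 1 SD goes from 80% to 79% (5:5), 77% (6:4), 72% (7:3) and 60% (8:2). The cost is a single degree of freedom only when the sequences are equal.

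**How large a period effect the design invites.** The protocol limits it in three ways. At least 14 days without an adjustment precede the first trial period. Participants must have worn the existing ODRA 2.0 brace for several hours a day over the previous six months, which the protocol ties to a shorter fitting period. KOOS is completed at delivery and at the first trial meeting, so it is familiar before either trial period starts.

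**The case for a change.** The strongest case for the concern is that the line does count factors, arrives at one, and is the only design or analysis statement shown. An analysis plan that followed it literally would omit period. The mechanism is real: the algebra and the simulations confirm lost power at 5:5 and bias at unequal splits. Conditional on an observed 8:2 split, the type I error of 10.5% to 20% is what matters to the person reading that trial, whatever the average over splits. The run-in and the prior brace experience may reduce a period effect, but nothing shows that they remove it.

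All of that stands as a reason to include a period term when the analysis is written. It does not show that the protocol excludes one. The missing sequence ratio is likewise detail that is not given: the protocol does not state simple randomisation, and an allocation list may well be balanced. The line could name period and sequence, but that would be a clarification of a label that is not wrong.

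**Conclusion.** The concern does not hold. The protocol names a crossover with one experimental factor and randomised order, which is a correct description of the design. It fixes no analysis, so it cannot be faulted for fixing one without a period term, and the choice of terms is commonly left to the statistical analysis plan, which was not available.

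The size of the problem, had it existed, depends on a period effect that the protocol does not quantify. At 0.25 SD and 5:5, ignoring period costs about one power point; at 0.5 SD it costs seven (79% to 72%) and at 1 SD thirty-one (79% to 48%). Type I error is conservative at 5:5 and 6:4, slightly raised at 7:3, and clearly raised only at 8:2 or worse, an 11% event if randomisation is simple. These figures assume normal errors, no carryover, all 10 participants analysed, two-sided alpha 0.05 and, for power, a true effect of 1 SD. The conclusion that nothing is misspecified rests on the text alone and on none of these assumptions.

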Protocol for the clinical validation of a valgus knee brace for gonarthrosis

Presented to the Véritas IRB Research Ethics Committee

TOPMED

Version 02

Approved in French on March 27th 2023

Translated on June 25th 2025

NCT05814471

SCHEDULED START AND END DATES

From March 2023 to March 2024

RESEARCH PROJECT DESCRIPTION

Issues

Valgus knee braces (VKB) is one form of treatment to help patients suffering from gonarthrosis. The aim of this form of treatment is to compensate for certain biomechanical deficits in patients. A multitude of joint arrangements are available to target specific biomechanical deficits. A constant challenge for orthosis manufacturers is to transmit the biomechanical effect of the orthosis to the patient. The desired effect requires a change in the forces applied inside the knee, but the orthosis cannot directly transmit the forces to the patient's bones due to its external nature. Orthotic customization is essential to improve the transmission of the biomechanical effect, as well as tolerance to it. Comfort, ease of fitting and effectiveness are essential components a quality orthosis. With this in mind, Laboratoires Victhom Inc. would like to test its new knee brace attachment system.

State of knowledge and project relevance

There are 2 main types of orthosis for gonarthrosis: soft and rigid. Soft orthoses use malleable materials such as fabric or rubber to apply forces to the leg, while rigid orthoses use plastic or metal braces. What's more, three main types of fastening system are used on these types of orthoses: velcro, hybrid and cable-tied. Different configurations are therefore used to compensate for the biomechanical deficits attributable to the pathology.

Each fastening system has its advantages and disadvantages. Velcro fasteners are quick and intuitive to use, but there are a number of issues that come up when using them: adjustment difficulties, cleaning the system, the number of straps needed to hold the leg in position, and the noise produced when the velcro is released. Hybrid systems regularly contain velcro fasteners, to which quick-release fasteners have been added to simplify strap installation and removal. However, they retain most of the disadvantages of velcro systems. Cable tightening systems also feature quick-release fasteners. The advantage of cable clamping is that belts can be adjusted easily and precisely, with minimal noise.

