An electronic diary will be completed each day for the duration of wear of each orthotic condition. The diary will detail total wearing time, as well as sitting time, physical and sporting activities performed during the day, number of orthosis removals and adjustments, discomfort experienced and medication taken.

Questionnaires :

A questionnaire containing general information: age, sex, height, weight, whether they wear a knee brace on both legs, and the length of time since they purchased their personal brace. This questionnaire will be completed at the first trial meeting.

A subjective questionnaire (Satisfaction) will be completed by participants to assess the ease with which they put on and take off the brace, and to validate the comfort, fit and aesthetic appearance of the brace. This questionnaire will be completed 5 or 6 times, depending on the order of the participant's conditions.

A Quebec version of the Knee injury and Osteoarthritis Outcome Score (KOOS) questionnaire will be used to quantify the evolution of the participant's symptoms and their effects on quality of life. This questionnaire will be completed 4 times (delivery meeting and trial meetings 1 to 3).

A Quebec version of the Psychological Symptoms Inventory (Ilfeld 1976), abbreviated ISP hereafter, will be used to quantify the evolution of participants' psychological symptoms. This questionnaire will be completed 4 times (delivery session and trial sessions 1 to 3)

At each session, participants showing a clinically significant interpretation of their total score, anxiety (questions 2, 3, 9, 11, 13, 15, 16, 20, 22, 23, 29), depression (questions 1, 5, 6, 8, 10, 14, 18, 19, 21, 24), hostility (questions 12, 25, 26, 27) or concentration (questions 4, 7, 17, 18) will be contacted by e-mail to offer them mental health resources. Participants who chose an answer other than "never" to question 24 will also receive this e-mail. Links to these resources can also be found at the end of the questionnaire.

A fastening system comparison questionnaire will be completed at Trial 3 to ascertain participants' preferences regarding the installation and de-installation process, as well as their orthotics.

Photos of the fitted leg wearing the orthosis will be taken 5 or 6 times, depending on the order of the participant's conditions.

Estimated duration of participants' activities

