pattern analysis data is confidential and will be used only for the purposes of this research project, unless otherwise agreed by the participant. All data collected, notes, photos and computer recordings are encrypted on servers. Unless required by law, no information that could directly or indirectly reveal your identity will be disseminated or published without your prior explicit consent.

All questionnaires and digital logs have been created using the Lime Survey platform. The information processed is hosted in Canada on the platform's encrypted servers (Secure Socket Layer procedure), which comply with the RGPD standard.

Data will be stored in coded form for a period of five (5) years, then anonymized in a database for retention for a period of ten (10) years for statistical reference purposes.

CONTINUOUS EXAMINATION

Should any inconvenience arise following the completion of the prototype validation test, participants will be promptly notified.

DISSEMINATING RESULTS

No disclosure to patients will be made following the trials.

Results will not be published.

COMPENSATION

If necessary, a parking sticker will be provided to participants during their visit. A compensation of \$50 will be given for their participation in each meeting of the validation protocol. The total amount awarded may not exceed \$350, equivalent to the full protocol with 2 adjustment meetings. The first payment will be made after the first trial meeting. The remainder of the amount will be distributed at the last meeting or when the participant chooses to end his or her participation.

RESPONSIBILITY

The legal rights of each participant will be maintained.

PROTOCOL SEQUENCE

First contact

Email to candidates

- *0241_VICD_Courriel_Recruitment*

Admission

Demonstrate interest by responding to e-mail/phone call

Sending documents and explanations :

- *0241_VICD_CourrielFIC*
- *0241_VICD_Consent_form*

Receipt of signed consent

Telephone contact for impression appointment

COVID call

Self-evaluation confirmation 24 hours before each meeting.

Impression meeting

45-minute meeting at the balance clinic

Anthropometric measurements of the thigh and digital impression taken

Delivery meeting

Meeting at the Balanced Clinic 1h45

Questionnaires: Satisfaction + KOOS + ISP

- *0241_VICD_Questionnaire_Satisfaction*
- *0241_VICD_Questionnaire_KOOS*
- *0241_VICD_Questionnaire_ISP*

Photos

Adjustment meeting

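### The ISP key puts question 18 in both depression and concentration and question 28 in no subscale, very probably an 18-for-28 slip in concentration

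*Protocol*

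**What the plan says.** Under *Measurement, assessment and data collection tools – Questionnaires*, the Protocol says that the ISP is completed four times, at delivery and at trial meetings 1 to 3. It then gives the question numbers of each subscale:

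- First subscale listed: "anxiety (questions 2, 3, 9, 11, 13, 15, 16, 20, 22, 23, 29"
- Second subscale listed: "depression (questions 1, 5, 6, 8, 10, 14, 18, 19, 21, 24"
- Third subscale listed: "hostility (questions 12, 25, 26, 27"
- Fourth subscale listed, with the action that follows: "concentration (questions 4, 7, 17, 18) will be contacted by e-mail to offer them mental health resources"

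A clinically significant result on the total or on any one subscale leads to the e-mail. A separate rule says that anyone who gives an answer other than never "to question 24 will also receive this e-mail". Everyone also has access to the resources through the form itself: "Links to these resources can also be found at the end of the questionnaire".

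The Protocol does not give the number of ISP questions, the answer scale, the cut-offs or the published scoring key. It does not say that a question may count in two subscales or that any question is left unscored.

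**The concern.** Question 18 is in two lists and question 28 is in none, with no explanation. The two numbers differ by one digit, which suggests a typing or transcription error.

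The lists are an operating rule for a participant-protection step, applied at every session. If the key is wrong and is followed as printed, one subscale is mis-scored whenever a participant answers questions 18 and 28 differently. A participant who should get the e-mail through that branch could then be missed, or one could be sent without need. The same subscale would also be wrong in the record of how psychological symptoms change over the trial.

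**Working it through.** **Inputs.** The four lists and the four administrations come from the Protocol's *Questionnaires* text. The 10 participants come from its section on participation of human participants.

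**Step 1: count the entries.** Anxiety 11, depression 10, hostility 4, concentration 4. The sum is 11 + 10 + 4 + 4 = 29, and the highest question number listed is 29.

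**Step 2: invert the lists.** Each question is shown with its subscale (A anxiety, D depression, H hostility, C concentration).

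| Questions | Subscale |
|---|---|
| 1–10 | D, A, A, C, D, D, C, D, A, D |
| 11–20 | A, H, A, D, A, A, C, **D and C**, D, A |
| 21–29 | D, A, A, D, H, H, H, **none**, A |

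Twenty-seven questions appear exactly once, question 18 appears twice and question 28 does not appear. That is 28 distinct questions in 29 entries.

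**Step 3: test the single-substitution explanation.** All four lists are printed in ascending order. Putting 28 in place of 18 in either list that contains it removes both the duplicate and the gap:

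| List changed | Result | Each question 1–29 used once | Still ascending |
|---|---|---|---|
| Concentration | 4, 7, 17, 28 | yes | yes |
| Depression | … 14, 28, 19 … | yes | no |

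Order therefore favours concentration as the place of the slip.

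**Step 4: size of the scoring error.** Let *n* be the number of items in the affected subscale, *K* the number of answer levels scored 0 to *K* − 1, and *d* the difference in levels between the answers to questions 18 and 28. With equally weighted items, the error as a percentage of the subscale maximum is

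100 × *d* / (*n* × (*K* − 1)).

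The Protocol gives neither *K* nor the weighting, so *K* = 4 and *K* = 5 are assumptions.

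| Slip in | *n* | *K* | *d* = 1 | *d* = 2 | *d* = 3 | *d* = 4 |
|---|---|---|---|---|---|---|
| Concentration | 4 | 4 | 8.3 | 16.7 | 25.0 | – |
| Concentration | 4 | 5 | 6.25 | 12.5 | 18.75 | 25.0 |
| Depression | 10 | 4 | 3.3 | 6.7 | 10.0 | – |
| Depression | 10 | 5 | 2.5 | 5.0 | 7.5 | 10.0 |

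For example, concentration with *K* = 4 and *d* = 1 gives 100 × 1 / (4 × 3) = 8.3. The error is zero when the two answers agree, and it can go in either direction.

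**Step 5: reach.** At most 10 × 4 = 40 administrations are scored with this key. There are 1 (total) + 4 (subscales) + 1 (question 24) = 6 routes to the e-mail. A single slip affects one of them, provided the total is summed over all questions and not built by adding the printed subscales.

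No cut-off is given, so the number of e-mails that would change cannot be computed.

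**The case against.** The duplicate and the gap are beyond dispute, but the rest is inference. No scoring key is shown. An instrument could share question 18 between two subscales and leave question 28 unscored, and nothing in the text rules that out. Two separate slips are also possible: question 28 could have dropped out of hostility or anxiety, with a stray 18 added elsewhere, and then different branches would be affected. These readings remain possible but are less economical. Each needs two departures that happen to leave the entry count equal to the highest question number. The same check against the key would settle all of them.

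The stronger objection concerns conduct. The title block says "Translated on June 25th 2025". The approved text is French and dates from March 2023, and the scheduled end was March 2024. The English line therefore cannot have governed scoring over the scheduled period, and the slip may exist only in the translation. The confidentiality section says "All questionnaires and digital logs have been created using the Lime Survey platform", but nothing describes how scores were computed. This stands. It is the reason any rescoring depends on what was actually used.

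The consequence is also small. The ISP serves none of the three research questions, the e-mail only offers resources, and the question 24 rule works independently. The percentages rest on assumed answer scales. All of this limits the importance of the point but does not make the printed key right.

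**Conclusion.** The point holds and is minor. It is certain from the text that question 18 is listed twice and question 28 not at all. It is very probable, but not proven, that concentration should contain 28 instead of 18.

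On that reading, one of four concentration items is wrong as written. Under the assumed scoring, the subscale is off by about 6 to 25 percentage points of its maximum when the two answers differ. If the slip is in depression, one of ten items is wrong and the range is 2.5 to 10 points. The number of administrations actually mis-scored is unknown and cannot exceed 40.

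The anxiety and hostility branches and the question 24 rule are untouched, as is the total if it sums all questions. No estimate in the comparison of the two fastening systems changes.

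**What to change.** 1. Check the four lists against the scoring key of the Quebec ISP version and against the approved French protocol.
2. Correct the line, probably to concentration = 4, 7, 17, 28. If the key really does share question 18 and leave question 28 unscored, say so in the text.
3. Find out whether the scoring actually used carries the same slip. Only if it does, rescore the affected subscale and recheck that branch of the contact rule.

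The cost is one number in one line and a check of the scoring. No new data are needed. The worst case is rescoring one subscale for at most 40 administrations. Coded data are to be kept for five years, so a recheck should be possible.

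### Is it a fault that the protocol randomises the order of the two fastening systems without fixing a 5:5 split among ten participants?

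*Protocol*

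**What the plan says.** Under 'Type of test' the protocol describes a crossover with one factor, the attachment system, at two levels. There are therefore two possible orders: Velcro then cable, or cable then Velcro. Under 'Estimated duration of participants' activities' it says: "The order of attachment system conditions is randomized for participants". The first system is installed at the first trial meeting, after a fitting period about which the protocol says: "This wearing period will always be performed using the Velcro fastening system currently available on the market".

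The section on participants gives the sample size: "10 adult participants will be recruited to test the different orthoses". The consent section allows withdrawal at any time and adds that "all material allowing the identification of the participant and the data provided will be destroyed, unless the participant authorizes the researcher to use them".

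The protocol states no allocation ratio, block size, list or concealment procedure. It also gives no power, effect size, standard deviation or drop-out rate.

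**The concern.** In a two-period crossover, equal numbers in the two orders do two useful things. A difference between period 1 and period 2 cancels from the simple mean of the within-person differences, and a period-adjusted estimate has its smallest variance. With ten participants, independent coin tosses often miss 5:5, sometimes by a wide margin. An analysis plan can add a period term, but it cannot restore balance once people have been allocated.

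A period difference is plausible here. Everyone receives a new brace, the comfort and ease-of-fitting ratings are subjective, and they may drift as wearers get used to the brace. No washout is described. Withdrawals, whose data are destroyed by default, could make an uneven split worse. What would be at stake is the precision of the cable-versus-Velcro comparison and, in the one trial actually run, a shift in an unadjusted estimate. The remedy would cost one sentence and one prepared list.

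**Working it through.** The protocol has no figure of its own to reproduce.

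**Inputs.** From the protocol: n = 10, two orders, order randomised. Assumed, because the protocol does not give them: simple 1:1 randomisation, normal paired differences with SD 1, a period effect common to all participants, no carryover, a two-sided 5% test, and a true system effect of 1 SD.

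**Model.** Let D be cable minus Velcro within a person, τ the system effect and π the period 2 minus period 1 difference. Then D = τ + π + error for Velcro-first and D = τ − π + error for cable-first.

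**Chance of each split**, Binomial(10, 0.5):
- 5:5: 252/1024 = 24.6%
- 6:4: 2 × 210/1024 = 41.0%
- 7:3 or worse: 34.4%
- 8:2 or worse: 10.9%
- 10:0: 2/1024 = 0.2%

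**Consequence of each split.** The unadjusted shift is π × |n₁ − n₂|/10. The adjusted variance is ¼(1/n₁ + 1/n₂). Power is from the noncentral t with 8 df.

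| Split | Unadjusted shift | Adjusted variance | Efficiency against 5:5 | Power, 1 SD |
|---|---|---|---|---|
| 5:5 | 0 | 0.1000 | 100% | 79% |
| 6:4 | 20% of π | 0.1042 | 96% | 77% |
| 7:3 | 40% of π | 0.1190 | 84% | 72% |
| 8:2 | 60% of π | 0.1563 | 64% | 60% |

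**Is validity affected?**
- Unadjusted estimate: the sign attached to π is +1 or −1 with probability ½ each, so its expectation is zero and the estimate is unbiased over the randomisation. The mean absolute shift is 24.6% of π, but the size of π is unknown.
- Period-adjusted estimate: half the sum of the two order means is ½[(τ + π) + (τ − π)] = τ. No period effect remains at any split that has someone in each order.
- Type I error stays at about 5%.

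**Average cost.** Efficiency at a given split is 4n₁n₂/100. Under simple randomisation E(n₁n₂) = 10 × 9/4 = 22.5, so mean efficiency is 4 × 22.5/100 = 90%. That is a loss of about one participant in ten. Average adjusted power against 5:5, counting 10:0 as zero, is:
- 0.8 SD: 55.6% against 60.3%
- 1 SD: 74.1% against 79.1%
- 1.2 SD: 87.2% against 91.2%

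If π is zero and a plain paired t-test is used (9 df), power for 1 SD is 80.3% at every split, and a 5:5 list gains nothing.

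**What a 5:5 list would secure.** It guarantees balance only if all ten are allocated and analysed. Two random losses from 5:5 leave 5:3 with probability 2 × 0.222 = 0.44. Three leave 5:2 with probability 2 × 0.083 = 0.17. The same probabilities apply if people leave during fitting and the last entries of a ten-item list are never used.

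**The case for a change.** The strongest case for keeping the point is that sequence balance is settled at allocation, so it cannot be left to an analysis plan. The allocation ratio and method are usually protocol matters, and nothing in this protocol supplies them. Under simple randomisation a split of 7:3 or worse occurs about one time in three. At 7:3 a period-adjusted analysis loses 16% of the information, and at 8:2 it loses 36%. A list also limits the damage from withdrawals: after two random losses it leaves 5:3 at worst, whereas simple randomisation leaves 6:2 or worse with probability 2 × (1 + 8 + 28)/256 = 28.9%. The price is close to nothing.

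The arithmetic stands, and so does the advice as good practice. It does not show that the protocol says anything wrong. The losses follow from a method the protocol does not name, and a block size or list is often kept in a separate randomisation document, which is not shown here. Nor would a 5:5 list deal with the more distinctive feature of this design, the Velcro-only fitting period. With it the orders become Velcro–Velcro–cable and Velcro–cable–Velcro, and balance cancels only a period effect common to both; it does not remove that asymmetry or any carryover. A fixed list also has a small cost of its own: on average 1.7 of the ten assignments can be predicted by someone who knows the earlier ones.

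**Conclusion.** The concern does not hold. Randomising the order is the correct choice for this crossover, it is stated, and it is contradicted nowhere. What is absent is detail of the allocation method, which the trial team or a randomisation document would ordinarily supply.

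If a balanced list is in use, nothing is lost. If simple randomisation is used, a trial run as written still gives an estimate that is unbiased over the randomisation, with a type I error of about 5%. The average price is then 10% of the information, or 4 to 5 points of power for effects of 0.8 to 1.2 SD. The power figures rest on normal paired differences, a common period effect, no carryover and a two-sided 5% test, none of which the protocol states. A bad draw such as 8:2 would cost more, but it remains a matter of precision, and of conditional bias if period is ignored, not of a wrong plan. A 5:5 list is a preference; the protocol needs no correction on this point.
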